7.2. Study-specific evaluations and procedures

7.2.1. Laboratory diagnosis for Huntington's disease (PCR)

Where applicable, laboratory diagnosis of Huntington's disease will be carried out using the PCR methodology (*polymerase chain reaction*) during the visit (V-3), as published by Warner and collaborators (1993). The strategy of the genetic analysis used will be the determination of the number of repetitions of the CAG trinucleotide, contained in the 5' region of the IT15 gene, in 4p16 by PCR (sequencing).

7.2.2. Clinical evaluation: demographic data, medical history and physical examination

Participants will be clinically evaluated by the study physician, and the following items should be evaluated and recorded in the source document:

- a. Demographic data (birth date, gender and race);
- b. Medical history:
- History of current pathology Huntington's disease:
 - ✓ Start date;

✓ Evolution of signs/symptoms (includes motor, oculomotor, cognitive and psychiatric changes;

➤ Background:

- ✓ Personal history (other diagnoses/pathologies, dates and clinical evolution);
- √ Family history;
- c. Physical examination and vital data:
- Physical examination assessment:
 - ✓ General State: the participant may be in good general condition (GGC), regular general condition (REG) or bad general condition (BGC);
 - ✓ The following should be evaluated: the degree of mucosal staining, hydration, perfusion (e.g., but not restricted to: clinical signs of cyaniasis) and respiratory pattern.
 - ✓ Overall assessment: includes cardiovascular, pulmonary, digestive, osteomuscular and peripheral systems, with emphasis on neurological and other evaluation, if necessary.

Evaluation of vital signs data:

- ✓ Weight: preferably measured on a calibrated digital scale. At the time of measurement, the participant must be wearing light clothing (without wearing shoes and empty pockets). Body weight will be recorded in kilograms (Kg);
- ✓ Height: a statometer (retractable train) attached to the digital scale will be used. During the procedure, the participant should be barefoot (or wearing socks) and position himself in the center of the equipment in an upright posture looking at a fixed point at eye height, with arms extended to the side of the body and palms facing back. The reading recorded after the measurement will be given in meters (m);
- ✓ BMI: will be determined by the BMI equation = weight/height² (kg/m²). According to the value found, the participant is categorized as thinness, eutrophy, overweight and degrees of obesity;
- ✓ Blood pressure (BP): should be performed after the participant has remained at rest (without any physical effort) for at least 5 minutes. After this period, it will be checked 3 times at intervals of 1 to 2 minutes using a calibrated digital device. The measurement of the first measurement will

be discarded and the average of the last 2 measurements performed (ABP) will be recorded in a source document using the unit of measurement of millimeters of mercury (mmHg);

- ✓ Heart rate (HR): includes checking the frequency (number of palpated or ascultated pulses), rhythm (regularity of heartbeat) and amplitude (quality of pulses felt). This parameter will be measured by palpation of the radial artery. The result will be reported using the bpm unit of measurement (beats per minute);
- ✓ Body temperature: the measurement of the parameter will be performed using calibrated digital thermometer. The unit of measure used will be the centigrade scale, commonly called degrees Celsius (°C).

7.2.3. Laboratory tests and serology

The tests to be performed in the study are described below. In visits in which there is the administration of the product, samples for laboratory tests should be collected before the beginning and after 06h 00min of the end of product administration.

Table 03. Laboratory tests to be performed on V-3 and in all post-cycle follow-up visits (V3, V7, V11)

Category	Test	Normality values	
Hematological Analysis	Hemogram (erytrogram, leukogram and platelet count)		
	Serum sodium		
Biochemical Analysis	Serum potassium		
	Amylase		
	Total cholesterol and fractions (LDL, HDL and VLDL)		
	Triglycerides	According to the reference	
	Coagulogram (RNI, TAP and TTPA)	values established by the laboratory.	
	Alkaline phosphatase		
	Glycated hemoglobin (HbA1c)		
	Urea		
	Uric acid		
	TGO		
	TGP		
	Gamma-GT		

Category	Test	Normality values
	Total bilirubin and fractions	
	Serum creatinine	
	CK	
	CKmB	
Urological Analysis	Urine summary (urine I)	
Other	β-hCG urinary (women-only)	

Table 04. Serological tests to be performed in the study at visits V-3 and V11.

	HIV (1 + 2) (Anti-HIV-1.2)	
	HTLV I and II	
Serological Analysis	HBV (HbsAg and Anti-HBc)	Negative
	HCV (anti-HCV-Ab)	
	FTA-ABS (syphilis)	

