a Items "d" and "e" of the inclusion criteria will be evaluated only at the inclusion visit (V-3) due to the natural fluctuation of the disease b For participants who need to carry out the laboratory diagnosis of Huntington's disease, the test will be performed at V-3 and

evaluated at V-2

Clinical Protocol: ADORE-DH Sponsor: Cellavita Pesquisa Cinetífica LTDA Amendment 6 dated February 23, 2021.

VII. Framework of study activities - Treatment and Follow-up Period

Activities	V0 Start of treatment - Up to 30 days after V-1	V1 30+5 days after V0	V2 60+5 days after V0	V3 90+5 days after V0	V4 120+5 days after V0	V5 150+5 days after V0	V6 180+5 days after V0	V7 210+5 days after V0	V8 240+5 days after V0	V9 270+5 days after V0	V11 300+5 days after V0	V11 ^c 330+5 days after V0
	1 st adm. Cycle 1	2 nd adm. Cycle 1	3 rd adm. Cycle 1	F-up.	1 st adm. Cycle 2	2 nd adm. Cycle 2	3 rd adm. Cycle 2	F-up.	1 st adm. Cycle 3	2 nd adm. Cycle 3	3 rd adm. Cycle 3	Final
Evaluation of inclusion criteria/ Exclusion (except criteria "d" and "e")	Х											
Evaluation of discontinuation criteria		Х	Х	Х	Х	X	Х	Х	X	Х	Х	Х
Medical evaluation: medical history and physical examination/vital data	Х	х	Х	Х	Х	Х	Х	Х	X	Х	Х	Х
Randomization	Х											
Intravenous administration of Cellavita-HD or placebo (hospitalization for a period prior to administration and for another 06 hours)	Xª	Xª	Xª		Xa	Xª	Xa		Xa	Xa	Xa	
Blood and urine collection for laboratory tests				Х				Х				Х
Evaluation of laboratory test results					Х				X			Х
Pregnancy urinary test for women	Х	Х	Х	Х	Х	Х	Х	Х	Х	Х	Х	Х
Blood collection for serology												Х
Evaluation of serology result												Х
ECG performance				Х				Х				Х
Evaluation of ECG result					Х				Х			Х
ECG monitoring	Х	Х	Х		Х	Х	Х		Х	Х	Х	
UHDRS and HAM-D scale and CIBIS	Х	Х	Х	Х	Х	Х	Х	Х	Х	Х	Х	Х
MRI for CNS evaluation												Х
Evaluation of CNS MRI result												Х

Clinical Protocol: ADORE-DH

Sponsor: Cellavita Pesquisa Cinetífica LTDA Amendment 6 dated February 23, 2021.

Activities	V0 Start of treatment - Up to 30 days after V-1	V1 30+5 days after V0	V2 60+5 days after V0	V3 90+5 days after V0	V4 120+5 days after V0	V5 150+5 days after V0	V6 180+5 days after V0	V7 210+5 days after V0	V8 240+5 days after V0	V9 270+5 days after V0	V11 300+5 days after V0	V11 ^c 330+5 days after V0

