- Verification of discontinuation criteria (item 5.2.3);
- Medical evaluation: updating of medical history and personal history and general physical examination/vital signs (Item 7.2.2 and 7.2.8) with BMI assessment;
- Intravenous administration of the investigational product at the given dose or placebo;
- Hospitalization for a period prior to administration and for another 06 hours after the end of the administration (the length of hospitalization may be extended at the discretion of the Principal Investigator);
- ECG monitoring during hospitalization time (during 06 hours after IP administration) (Item 7.2.4);
- Application of the UHDRS, HAM-D and CIBIS scales (Item 7.2.5 to 7.2.7);
- Record of adverse events (AEs) and concomitant medications;
- Assessment of pregnancy risk and dispensation of contraceptive method, if applicable;
- Performance of β-hCG in women;
- General guidelines.

G) Visit 6 (V6): 3rd administration of cycle 2 (180 + 5 days after V0)

- Verification of discontinuation criteria (Item 5.2.3);
- Medical evaluation: updating of medical history and personal history and physical examination/vital signs (Item 7.2.2 and 7.2.8) with BMI assessment;
- Evaluation of the results of laboratory tests performed at the previous visit;
- Intravenous administration of the investigational product at the given dose or placebo;
- Hospitalization for a period prior to administration and for another 06 hours after the end of the administration (the length of hospitalization may be extended at the discretion of the Principal Investigator);
- ECG monitoring during hospitalization time (during 06 hours after IP administration) (Item 7.2.4);
- Application of the UHDRS, HAM-D and CIBIS scales (Item 7.2.5 to 7.2.7);
- Record of adverse events (AEs) and concomitant medications;
- Assessment of pregnancy risk and dispensation of contraceptive method, if applicable;
- Performance of β-hCG in women;
- General guidelines.

H) Visit 7 (V7): follow-up visit (210 + 5 days after V0)

- Verification of discontinuation criteria (Item 5.2.3);
- Medical evaluation: updating of medical history and personal history and physical examination/vital signs (Item 7.2.2 and 7.2.8) with BMI assessment;
- Collection of blood and urine samples for testing:
 - Laboratory tests (Item 7.2.3 Chart 3);
- ECG 12 leads performance (Item 7.2.4);
- Application of the UHDRS, HAM-D and CIBIS scales (7.2.5 to 7.2.7);
- Record of adverse events (AEs) and concomitant medications;

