9.6.1. Suspension of administration of the investigational product

If after the first administration there is a suspicion of the occurrence of an adverse event that may possibly threaten the participant's life, the Medical Investigator of the ADORE-DH project should judge whether the treatment should be discontinued or suspended indefinitely. Among such events, it may be considered (not restricted to):

- Systemic Inflammatory Response Syndrome (SIRS);
- Anaphylactic shock or allergic reaction;
- Significant reduction in total platelet count and granulocytic cells (neutrophils, eosinophils and basophils);

 Prolongation of prothrombin (TP) time and activated partial thromboplastin (TTPa);

The suspension of the administration to a participant due to the occurrence of one of the events mentioned above must be informed to Sponsor within a maximum period of 24 hours and notified to the Research Ethics Committee.

The safety assessment should be carried out at each visit in which the drug of the study takes place.

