#### 4.2.3. Laboratory Test

Laboratory tests collected in the study and recorded in the eCRF are described in protocol Section 7.2.3 and indicated below.

- Hematology: RBC, Hemoglobin, Hematocrit, MCV, MCH, MCHC, RDW, WBC, Segmented, Typical Lymphocytes, Monocytes, Eosinophils, Basophils, Platelets, MPV.
- Chemistry: PT, INR, APTT, APTT Ratio, Glycated Hemoglobin, Amylase, Uric Acid, Total Bilirubin, Direct Bilirubin, Indirect Bilirubin, Triglycerides, Total Cholesterol, HDL, VLDL, LDL, Non-HDL, CKMB, CPK, Creatinine, Alkaline Phosphatase, Gamma GT, Potassium, Sodium, AST, ALT, Urea.
- Urinalysis as indicated on the eCRF.

Sponsor: Cellavita Pesquisa Científica Ltda.

Protocol: ADORE-DH

Statistical Analysis Plan

Version: 1.0

- Other β-hCG urinary (women-only).
- Serology: HIV (1 + 2) (Anti-HIV-1.2), HTLV I and II, HBV (HbsAg and Anti-HBc), HCV (anti-HCV-Ab) and FTA-ABS (syphilis).

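### Protocol 7.2.3 orders laboratory samples before and 6 h after every infusion, but the schedule lists draws only at V-3, V3, V7 and V11; a site following the schedule has no blood count or clotting test in 6 of 8 inter-infusion intervals

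*Protocol*

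**What the plan says.** Protocol 7.2.3 states, for visits with product administration, that "samples for laboratory tests should be collected before the beginning and after 06h 00min of the end of product administration". The caption of Table 03, directly below, reads "Laboratory tests to be performed on V-3 and in all post-cycle follow-up visits (V3, V7, V11"; the table holds the hemogram and the coagulogram.

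The rest of the plan follows the caption:

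- In the activity framework (Protocol VII), the row "Blood and urine collection for laboratory tests" is marked at V3, V7 and V11 and is blank at all nine infusion visits. SAP section 3 reproduces it with the same marks.
- The visit lists give a draw at V-3 (7.3.1) and at V3, V7 and V11 (7.3.3), and none at V0, V1, V2, V4, V5, V6, V8, V9 or V10.
- Protocol 8.7.1.1.3 places the safety assessment at the end of each cycle.

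The Visit 6 list includes "Evaluation of the results of laboratory tests performed at the previous visit", but the previous visit, V5, has no draw.

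The SAP does not choose between the rules. SAP 4.2.3 says "Laboratory tests collected in the study and recorded in the eCRF are described in protocol Section 7.2.3 and indicated below", and that section contains both.

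**The concern.** A site cannot tell from the documents whether blood is due on infusion days. If it works from the framework and the visit lists, it omits an ordered safety sample nine times over.

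The parameters matter for dosing. Protocol 9.6.1 lists, among events for which the investigator judges suspension, "Significant reduction in total platelet count and granulocytic cells" and "Prolongation of prothrombin (TP) time and activated partial thromboplastin (TTPa". Both are laboratory findings and can be clinically silent. Without infusion-day samples, nothing in the schedule looks for them between the infusions of a cycle.

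The laboratory analysis depends on the answer too. SAP 7.1 defines baseline as the last non-missing value before first treatment. That is the V0 pre-infusion sample if 7.2.3 was followed, and the V-3 sample if the schedule was. SAP 7.5.3 summarises change by scheduled visit and has no rule for a pre-infusion and a 6 h value at the same visit.

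**Working it through.** The plan gives no figure of its own to reproduce, so the check is a count on the nominal visit grid.

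**Inputs.** Infusions at days 0, 30, 60, 120, 150, 180, 240, 270 and 300, and follow-up draws at days 90, 210 and 330 (Protocol 4.5, Table 03). Thirty-five participants (4.3). Two samples per infusion (7.2.3).

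**1. Intervals between infusions, schedule only.** Nine infusions give 9 − 1 = 8 intervals.

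| Interval | Days | Scheduled draw inside |
|---|---|---|
| V0–V1 | 0–30 | none |
| V1–V2 | 30–60 | none |
| V2–V4 | 60–120 | V3, day 90 |
| V4–V5 | 120–150 | none |
| V5–V6 | 150–180 | none |
| V6–V8 | 180–240 | V7, day 210 |
| V8–V9 | 240–270 | none |
| V9–V10 | 270–300 | none |

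Uncovered: 6 of 8 (75%), all within a cycle.

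**2. First post-baseline result.** The V3 draw falls at day 90 (window to day 95), after the infusions at days 0, 30 and 60. Its evaluation is listed at V4, day 120 (window to day 125).

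**3. Number of draws.**
- 7.2.3, infusion days: 9 × 2 = 18 per participant; 18 × 35 = 630 in all.
- Schedule: 1 + 3 = 4 per participant; 4 × 35 = 140 in all, none on an infusion day.

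**4. What each kind of draw can show.**
- Pre-infusion draws at V1, V2, V5, V6, V9 and V10 put a draw in each of the six uncovered intervals, raising coverage from 2 of 8 to 8 of 8.
- Those draws come nominally 30 days after the preceding infusion. So do the scheduled ones: 90 − 60 = 210 − 180 = 330 − 300 = 30. Neither kind would show a change that recovers within 30 days.
- Only the nine 6 h draws could show such an acute change.

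**5. Consequence for the SAP tables.**
- If 7.2.3 was followed, post-baseline results per participant are 18 − 1 (V0 pre-infusion is baseline) + 3 = 20, against 3 under the schedule.
- Infusion visits with two post-baseline values: 9 − 1 = 8.
- If the schedule was followed, the laboratory baseline is V-3. Protocol 4.4 allows up to 90 days for that phase; the windows in 4.5 add to 37 + 37 + 30 = 104 days before V0.

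**The case against.** The best defence is that the 7.2.3 sentence is a drafting remnant and that one laboratory assessment per cycle is the design. The table caption, framework, visit lists, SAP copy and 8.7.1.1.3 all agree. Where infusion-day measurement was wanted, the plan says so: 7.2.4 asks for ECG on infusion days and the framework has an ECG monitoring row at all nine. SAP 7.5.5 gives before, during and after time points for vital signs, while 7.5.3 gives none for laboratory data. The V6 item looks like a copying slip; V11 has a similar one for ECG. This stands as evidence of likely intent. It does not settle the matter: no text withdraws the 7.2.3 sentence, and the last line of 9.6.1 asks for a safety assessment at every dosing visit.

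Second, the safety gap is narrow. Section 9.6.1 applies when "there is a suspicion of the occurrence of an adverse event that may possibly threaten" the participant's life; it sets no laboratory screening rule. A reader might infer that suspension could not operate, or that participants were re-dosed unchecked. The documents do not support that. Every infusion visit after V0 has a medical evaluation and a check of discontinuation criteria, which include laboratory conditions (5.2.3 h). Each infusion has 6 h of observation, extraordinary visits are available (7.4), and V3 and V7 results are read at V4 and V8. Protocol 9.5 also cites a meta-analysis with no significant association with acute infusion toxicity, though it adds that safety is not fully elucidated. This stands, and limits the point to silent changes.

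Third, the schedule change may come too late. SAP 4.1.2 describes the V11 MRI, after the last infusion, in the past tense for all participants. This also stands.

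**Conclusion.** The inconsistency is real, with minor to moderate consequences. A site following the schedule omits samples that 7.2.3 orders, so that 6 of 8 inter-infusion intervals have no scheduled blood count or clotting test and three infusions precede the first post-baseline result. Efficacy is unaffected.

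Three stronger readings go too far:

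- That the two rules exclude each other. Table 03 does not say the listed visits are the only ones, so the schedule omits infusion-day draws rather than forbids them.
- That the samples were not taken. The documents do not show which rule was followed.
- That the count measures risk. Multiplying by participants (6 × 35 = 210 of 8 × 35 = 280 repeat infusions) only restates 6 of 8; the plan gives no rate of silent cytopenia or clotting change.

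The count assumes all nine infusions and nominal days. Actual timing is unknown: SAP 7.4.1 says that visits departed from the schedule because of COVID-19. On the analysis side the effect is limited to the laboratory baseline and the change-by-visit table. The abnormality and worst-value tables already accept extra samples, because SAP 7.1 includes unscheduled data in abnormality analyses.

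**What to change.** **For any remaining infusions.** Add the hemogram and coagulogram, before and 6 h after infusion, to Table 03, the activity framework (and its SAP copy) and the infusion-visit lists in 7.3.3. Correct the V6 item. Have the previous infusion's 6 h result read before the next dose; with nominally 30 days or more between infusions this is feasible. Requiring the same-day pre-infusion result before dosing would be a new rule and should be optional: the product arrives ready for use (6.7) and the documents give no laboratory turnaround time.

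The cost is up to 18 samples per participant above the present schedule and none beyond what 7.2.3 orders, all within the existing hospital stay. Taking only the six within-cycle pre-infusion draws would be cheaper, but would leave acute, recovering changes unseen.

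**For the SAP, probably the only part still usable.** Check the eCRF version named in SAP section 1 for infusion-day laboratory values.

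- If they exist, add to 7.5.3 a summary before and after administration, as 7.5.5 does for vital signs. Keep the 6 h value out of the change-by-visit table, and state that the V0 pre-infusion sample, not V-3, is baseline. Cost: one table and two sentences.
- If they do not exist, report the omission as a deviation from 7.2.3. Cost: a deviation entry and a sentence in the study report. This changes no result, but tells the reader that acute within-cycle laboratory effects were not systematically assessed.

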#### 7.5.3. Laboratory Test Results

All Hematology and Chemistry laboratory data will be summarized by change and % change from Baseline to each post baseline scheduled visit. For Urinalysis change and % change will only be done for pH.

Analysis of hematology and chemistry abnormalities will include a summary of abnormalities between baseline and worst post baseline visits based on criteria indicated on eCRF (Abnormal CS, Abnormal NCS, Normal, Not Done).

In addition a shift Table will display changes in status from baseline to worst post-treatment value will be summarized. The order of determining worst will be abnormal clinically significant > abnormal not clinically significant > not done.

A shift Table will summarize Serology Tests between Non-Reactive and Reactive.

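### The SAP's laboratory abnormality and shift tables carry no direction, so no planned table counts, by dose, participants who crossed the lower platelet or granulocyte limit or the upper PT/aPTT limit

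*Protocol*

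**What the plan says.** **Standard for normality.** Protocol 7.2.3, Table 03, refers the laboratory panel to the reference "values established by the laboratory". The panel is taken at V-3, V3, V7 and V11.

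**Directions of interest.** Protocol 9.6.1 asks the investigator to judge whether to stop or suspend treatment when a possibly life-threatening adverse event is suspected. Its list opens with "Among such events, it may be considered (not restricted to"). Two laboratory items follow, each running one way: "Significant reduction in total platelet count and granulocytic cells (neutrophils, eosinophils and basophils") and "Prolongation of prothrombin (TP) time and activated partial thromboplastin (TTPa").

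**Planned laboratory displays (SAP 7.5.3).**
- Continuous: "All Hematology and Chemistry laboratory data will be summarized by change and % change from Baseline to each post baseline scheduled visit".
- Abnormality summary, baseline against worst post-baseline: "based on criteria indicated on eCRF (Abnormal CS, Abnormal NCS, Normal, Not Done").
- Shift table: "shift Table will display changes in status from baseline to worst post-treatment value will be summarized", with worst ranked "abnormal clinically significant > abnormal not clinically significant > not done".

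SAP 4.2.3 lists platelets and the white-cell lines under hematology, and PT, INR and APTT under chemistry, so all of them fall under these rules. SAP 7.1 bases analyses of change on scheduled visits and admits unscheduled visits only to analyses of abnormalities. SAP 5 rules out hypothesis tests on safety data.

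**The concern.** A laboratory reference range normally has two ends, and the protocol's laboratory examples each concern one of them. The SAP's categorical displays record whether a result was abnormal and how the investigator rated it, but not which limit it passed. A platelet count that falls below the range and one that rises above it are the same entry if both carry the same label.

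Safety data are not tested, so the descriptive tables are the laboratory comparison between doses. Protocol 2 describes the dose sought as one that gives maximum efficacy and is considered safe. The arms hold 14, 14 and 7 participants, so one or two individual falls can matter and will barely move a mean. A reader of the planned tables could not say how many participants per arm crossed the limit of interest.

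**Working it through.** The plan gives no figure to reproduce. The check has two parts.

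**1. What the SAP classes merge.** Take five direction-aware states: Normal, High-NCS, Low-NCS, High-CS and Low-CS. The SAP reduces them to Normal, NCS and CS. Not Done has no value and is left out.

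| Type of move | Possible | Under the SAP classes |
|---|---|---|
| Normal to abnormal | 4 | 2 cells; low and high cannot be told apart |
| High to low | 2 × 2 = 4 | 2 read as no shift (High-NCS to Low-NCS, High-CS to Low-CS); 2 appear as a change of class without direction |
| All reversals, both directions | 2 × 4 = 8 | 4 read as no shift |
| All changes of state | 5 × 4 = 20 | 4 read as no shift |

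With low/normal/high crossed with NCS/CS, all 4 high-to-low moves show as shifts and the 4 normal-to-abnormal moves keep separate cells. The normal-to-abnormal row matters most, because it needs no unusual baseline.

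**2. Whether another planned output supplies the count.**

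| Output | Keeps direction? | Counts limit crossings by dose? | Unscheduled visits? |
|---|---|---|---|
| Change and % change (SAP 7.5.3), with minimum and maximum (SAP 7.1) | Yes | No: a change or an extreme is not a count of crossings | No |
| Abnormality summary and shift table (SAP 7.5.3) | No | Counts abnormal results, either direction | Yes |
| Listings (SAP 7.1) | Yes | No: nothing is tabulated by dose | Yes, if on the eCRF |
| TEAE tables (SAP 7.5.2) | Only through the coded term | Counts reported events, not crossings | If recorded as an adverse event |

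No row gives the count. An abnormal result from an extraordinary visit (Protocol 7.4, prompted by adverse events or relevant symptoms) enters the direction-free displays but not the signed ones.

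**Illustration with assumed counts.** Suppose all participants start normal, *a* of 14 high-dose participants fall below the platelet limit, *b* of 7 placebo participants rise above it, and all are labelled NCS. The SAP shows *a*/14 against *b*/7 abnormal. These are equal whenever *a* = 2*b*: 2/14 = 1/7 = 14.3%, 4/14 = 2/7 = 28.6%, 6/14 = 3/7 = 42.9%. A low/normal/high table would show *a*/14 against 0/7 low. With *b* = 0 the SAP table does show a difference, but not its direction. The documents do not indicate how likely any such pattern is.

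**The case against.** The strongest reply is that the events that matter are counted elsewhere. Protocol 9.6.1 describes its items as adverse events, and SAP 7.5.2 tabulates participants with TEAEs by system organ class, preferred term, severity and relationship, in the treatment columns of SAP 7.1. Protocol 9.1 also links clinically significant laboratory changes to adverse-event recording, although its wording on timing is unclear. Direction is kept in the signed summaries, and with 35 participants and four scheduled panels individual falls can be found in the listings.

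Much of this stands, and it rules out several stronger readings:
- A reader might infer that every high-to-low move is recorded as no shift. Only 2 of the 4 are.
- A reader might infer that the SAP discards direction altogether. The continuous summaries and listings retain it.
- A reader might infer that life-threatening laboratory events would go uncounted. The documents do not support that: such events are adverse events, and results judged not clinically significant are not the events Protocol 9.6.1 describes.
- A reader might infer that Protocol 9.6.1 sets laboratory suspension limits. It gives open-ended examples for the investigator's judgement, with no numbers.
- A reader might infer that the worst-value rule cannot work because it does not choose between a high and a low NCS result. For the shift table as planned, either choice gives NCS.

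It does not supply the missing count. A fall labelled NCS has no clear route into the TEAE tables, an extreme is not a count, and inspecting listings is not a planned comparison between doses.

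**Conclusion.** The point holds as a limited gap in descriptive safety reporting. The categorical displays in SAP 7.5.3 merge low with high: 4 normal-to-abnormal moves share 2 cells, and 2 of 4 high-to-low moves appear as no shift. As a result, no planned table counts, by dose, participants who crossed the lower platelet or granulocyte limit or the upper PT/aPTT limit. Table 03 of the protocol is not at fault; it names the standard that SAP 7.5.3 does not carry into its tables.

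This rests on reading the four eCRF labels as the whole classification. The documents do not show whether the eCRF also holds high/low flags or reference limits. Alpha, power and the efficacy analysis are unaffected. It is a cheap improvement.

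**What to change.** In SAP 7.5.3:
- Add low/normal/high status against the laboratory's reference range to the abnormality summary and the shift tables, at least for platelets, white-cell lines, PT/INR and aPTT.
- Report worst-low and worst-high separately where both directions are possible.
- Include unscheduled visits, as SAP 7.1 already provides for abnormalities.
- Keep the CS/NCS label as a second classification.
- In the same edit, state where Normal ranks. The laboratory ranking of worst omits it, whereas the ECG ranking in SAP 7.5.4 ends with it.

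The cost is SAP wording, programming and some extra tables; no new participant data are needed. The documents do not say that a single laboratory was used or that the eCRF holds the limits. If it does not, they must be obtained from each laboratory used and matched to the results.
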